9.1.1.3. Analysis of Correlation

Spearman rank correlation coefficient will be calculated to determine correlation between RSV/A, RSV/B, hMPV/A, and hMPV/B, RSV IgG prefusion F protein-specific antibody titers, hMPV IgG prefusion F protein-specific antibody titers, and VLP core IgG specific titers at Day 0, Day 28, Day 180 and Day 365 across all vaccine groups.

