4.1. Brief Description

4.1.1. Main Trial Brief Description

The Phase 2a clinical trial of IVX-A12 is a randomized, observer-blind, placebo-controlled, dosage optimization, multi-center trial to evaluate the safety and immunogenicity of a single IM dose of two different formulations of IVX-A12 (IVX-A12a with diluent alone and IVX-A12d with MF59[®]) compared to placebo (diluent) in adults 60 to 85 years of age. The dosage level and formulation were selected based on the totality of the IVX-A12 nonclinical data and the interim safety and immunogenicity clinical data from the ongoing IVX-A12 Phase 1 clinical trial.

The main portion of this Phase 2a clinical trial will have three vaccine groups: Two IVX-A12 groups and one placebo group. The total amount of VLP in the two IVX-A12 groups will not exceed 300 µg of VLPs. IVX-A12a, IVX-A12d, or placebo will be administered as a single IM dose to older adult subjects enrolled into two age strata (adults 60 to 69 years of age and elderly adults 70 to 85 years of age). Eligible older adults will be randomized simultaneously to the different trial groups to ensure balance among the groups. This Phase 2a clinical trial includes a sentinel group of 40 subjects (16 subjects per active treatment group [n=32]; 8 subjects in the placebo group) to conservatively assess the 150 µg RSV/150 µg hMPV dosage level in combination with MF59[®]. Sentinel subjects were closely monitored for a minimum of 48 hours and, if no stopping rules were triggered, the remaining subjects were enrolled.

Approximately 250 subjects will be randomly allocated at a ratio of 2:2:1 to receive one of the two IVX-A12 formulations (IVX-A12a [N=100] or IVX-A12d [N=100]) or placebo (N=50), respectively. Subjects were also be stratified by age group (60 to 69 years of age and 70 to 85 years of age). The planned subject allocation to trial groups is provided in [Table 1](#).

Table 1

Group	Dosage Level	Total (N=250)*
A	IVX-A12a (unadjuvanted 150 µg RSV/ 150 µg hMPV)	100
B	IVX-A12d (150 µg RSV/ 150µg hMPV adjuvanted with MF59 [®])	100
C	Placebo [†]	50

[†] Placebo will be aqueous diluent

*Note: The stratified randomization will ensure balanced dosage level group assignment between the two age groups (60 to 69 years of age and 70 to 85 years of age, respectively).

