4.3. Determination of Sample Size

4.3.1. Main Trial Determination of Sample Size

Sample size for this trial is not based on any formal hypothesis testing. Analyses of safety and immunogenicity will be primarily descriptive in nature. An approximate total of 250 subjects (approximately 100 subjects in each of the IVX-A12 groups and 50 subjects in the placebo group) will be randomized. With 100 subjects in each IVX-A12, there is a 63.4% probability of observing at least 1 subject with an AE if the true incidence of the AE is 1% and 86.7% probability of observing at least 1 subject with an AE if the true incidence of the AE is 2%. The trial will have more than 90% power to detect a difference of 20% or more in seroresponse rate (SRR) or detect a 2-fold increase or more in GMT or GMFR (assuming standard deviation at $0.5 \log_{10}$), between the two IVX-A12 groups (or between the IVX-A12 group and placebo group), with a two-sided type-1 error rate at 0.05.

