7.1. General Methods

- No formal statistical hypotheses to be tested for the study. 95% confidence interval (CI) and p-value are presented for data nature.
- Unless otherwise specified, summaries will be presented by vaccine group, aggregate IVX-A12, and overall.
- Vaccine groups will be categorized as:
 - Main Trial:
 - 150 µg RSV/ 150 µg hMPV IVX-A12a (unadjuvanted)
 - 150 µg RSV/ 150 µg hMPV IVX-A12d (adjuvanted with MF59®)
 - Placebo
 - Observational Extension Trial:
 - 150 µg RSV/ 150 µg hMPV IVX-A12a (unadjuvanted)
 - Placebo

Aggregate IVX-A12 includes 150 µg RSV/ 150 µg hMPV IVX-A12a (unadjuvanted) and 150 µg RSV/ 150 µg hMPV IVX-A12d (adjuvanted with MF59®).

- All listings will display age, sex, and race.
- Continuous variables will be summarized using the number of observations (n), mean, standard deviation (SD), median, minimum, and maximum. Additionally, quartiles will be provided for continuous variables related to immunogenicity. The same number of decimal places as in the raw data will be presented when reporting minimum and maximum; 1 more decimal place than in the raw data will be presented when reporting mean, median, least squares, and quartiles; and 2 more decimal places than in the raw data will be presented when reporting SD. No more than 3 decimal places will be presented. For confidence intervals (CIs) for mean will be presented with the same decimal places as the mean. For p-values and correlations, 3 decimal places will be presented. P-values <0.001 and >0.999 will be presented as '<0.001' and '>0.999', respectively.
- Descriptive statistics for categorical/qualitative data will include frequency counts and percentages. The total number of subjects in each vaccine group and placebo will be used as the denominator for percentage calculations, unless stated otherwise in the table shell. All percentages will be presented with one decimal point, unless specified otherwise. For percentages equal to 100 will show as 100 rather than 100.0.

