The geometric mean ratio (GMR) of the titers and fold-rise for serum anti-RSV/A- versus RSV-B will be calculated as described in [section 9.1.1.1](#) for all scheduled visits. Similarly, GMR will be produced for the ratio of serum anti-hMPV/A versus hMPV/B. This analysis will be performed for the following:

- By vaccine group;
- By vaccine group and age subgroup analyses category.

The GMR of the fold-rise in IgG prefusion F protein-specific antibody titer (ELISA) versus the fold rise in NAbs at all post-baseline visits for RSV and hMPV. This analysis will be performed for the following:

- By vaccine group;
- By vaccine group and age subgroup analyses category.

This document is confidential.

The proportion of subjects with ≥ 4 -fold increase in serum anti-RSV/A-, RSV/B-, hMPV/A- and hMPV/B-specific NAb versus baseline for Days 180 and 365 will be analyzed similarly as described in [section 9.1.2](#) by vaccine group, by vaccine group and age subgroup analyses category, by vaccine group and baseline tertile, and by vaccine group, baseline tertile, and age subgroup analyses category.

A similar analysis will be repeated for the proportion of subjects with ≥ 8 -fold increase for all post-baseline visits in serum anti-RSV/A-, RSV/B-, hMPV/A- and hMPV/B-specific NAb, as described in [section 9.1.1.2](#), for the following:

- By vaccine group;
- By vaccine group and age subgroup analyses category.

Tertile analyses will not be completed for ≥ 8 -fold increase.

Reverse cumulative distribution (RCD) curves will be provided for baseline (Day 0) to Days 28, 180, and 365 for the following assays: RSV/A-, RSV/B-, hMPV/A-, hMPV/B-specific NAb and RSV and hMPV prefusion F protein-specific IgG antibody titers. RCD curves will be produced for the following:

[figure not shown]
- By vaccine group;
- By vaccine group and age subgroup analyses category.

Analysis of correlation will be repeated, as described in [section 9.1.1.3](#), for Days 180 and 365.

Outliers will be listed, as described in [section 9.1.1.4](#), for Days 180 and 365.

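### Post-vaccination Spearman correlations between assays pool the IVX-A12 groups with placebo, so they partly measure vaccination status and are distorted, usually upward

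*SAP*

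**What the plan says.** SAP 9.1.1.3 plans Spearman rank correlations among seven readouts: four neutralizing titers (RSV/A, RSV/B, hMPV/A, hMPV/B), two pre-F IgG titers and VLP core IgG. It asks for them for "titers at Day 0, Day 28, Day 180 and Day 365 across all vaccine groups". SAP 9.1.2 carries the same method to the later visits: "Analysis of correlation will be repeated, as described in" section 9.1.1.3, for Days 180 and 365. This is the same analysis, not a second problem.

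Placebo is inside the pool. SAP 4.1.1 says that the main trial "will have three vaccine groups: Two IVX-A12 groups and one placebo group", and the lists of vaccine groups in SAP 7.1 and 7.1.1 include placebo. Subjects are "randomly allocated at a ratio of 2:2:1", which SAP 4.3.1 gives as "approximately 100 subjects in each of the IVX-A12 groups and 50 subjects in the placebo group".

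SAP 7.1 sets a general default: "Unless otherwise specified, summaries will be presented by vaccine group, aggregate IVX-A12, and overall". That default yields where a section specifies something else, and 9.1.1.3 does. Neighbouring analyses in 9.1.2 list separate results by vaccine group, and the ANCOVA and logistic models in 9.1.1.1 and 9.1.1.2 carry vaccine group as a term. The visible text plans no within-group or group-adjusted correlation.

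**The concern.** Before dosing, randomization makes the groups exchangeable, so pooling at Day 0 is harmless. After dosing it is not. The protocol summary reports from the Day 28 interim analysis that IVX-A12a raised neutralizing and binding antibody to both viruses. About four fifths of the pooled sample is then displaced on both members of many assay pairs and one fifth is not. A rank correlation over that mixture combines the association between two responses among similarly treated people with the separation between vaccinated and unvaccinated people.

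A reader of an NAb v IgG, A v B strain or RSV v hMPV coefficient will normally want the first component. The pooled figure does not separate it from the second. Comparisons over time suffer too: a coefficient that rises from Day 0 to Day 28 and falls by Day 365 could simply follow the vaccine-placebo gap as it opens and closes, with the within-group association unchanged.

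**Working it through.** **Inputs.** From SAP 4.3.1: groups of 100, 100 and 50; SD 0.5 log10; planning difference to "detect a 2-fold increase or more in GMT or GMFR"; two-sided 0.05. The vaccinated fraction is 200/250 = 0.8. Not in the documents, and so assumed: mean shifts of 4- and 8-fold, unequal shifts, the within-group correlations, equal shifts in the two IVX-A12 groups, and bivariate normal log titers.

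**The plan's own figure.** The SAP states no figure for the correlations. Its power statement uses the same SD, fold difference and group sizes, and it reproduces for GMT:
- 100 v 100: SE = 0.5 × √(1/100 + 1/100) = 0.0707; 0.301/0.0707 = 4.257; power = Φ(4.257 − 1.960) = 98.9%.
- 100 v 50: SE = 0.5 × √(1/100 + 1/50) = 0.0866; 0.301/0.0866 = 3.476; power = Φ(3.476 − 1.960) = 93.5%.

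Both exceed the stated 90%.

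**Formula for the pooled coefficient.** Let d1 and d2 be the shifts in SD units, d = log10(fold)/0.5. Let r be the within-group Pearson correlation, and let the weights be w1 = 0.8 (vaccinated) and w0 = 0.2 (placebo). Then

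pooled ρ = 12 × Σ w_g w_h w_k Φ2( d1(g−h)/√2, d2(g−k)/√2 ; r/2 ) − 3,

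summed over g, h, k in {0, 1}, where Φ2 is the bivariate normal distribution function with correlation r/2. With no shift this reduces to the within-group value, (6/π) arcsin(r/2).

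**One case by hand: r = 0, both assays up 4-fold.**
- d = 0.602/0.5 = 1.204; d/√2 = 0.851; Φ(0.851) = 0.803.
- Mean rank position of vaccinated subjects: 0.8 × 0.5 + 0.2 × 0.803 = 0.5605. Of placebo subjects: 0.8 × 0.197 + 0.2 × 0.5 = 0.2578.
- 0.8 × 0.5605² + 0.2 × 0.2578² = 0.2647; 12 × 0.2647 − 3 = 0.176.

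Two unrelated responses therefore show a pooled coefficient of about 0.18.

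**Equal shifts on both assays:**

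| Within-group ρ | 2-fold | 4-fold | 8-fold |
|---|---|---|---|
| 0 (r = 0) | 0.052 | 0.176 | 0.306 |
| 0.288 (r = 0.3) | 0.325 | 0.413 | 0.506 |
| 0.483 (r = 0.5) | 0.510 | 0.574 | 0.642 |
| 0.786 (r = 0.8) | 0.797 | 0.825 | 0.853 |

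**Unequal shifts, from the same formula:**
- 1-fold v 8-fold: 0.483 falls to 0.395, and 0 stays at 0.
- 2-fold v 8-fold: 0.786 falls to about 0.76.

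A simulation of 600,000 draws per setting agrees with these values to within 0.002.

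**At the trial's size.** In 3,000 simulated trials of 100/100/50 with r = 0 and equal shifts, the pooled coefficient had p < 0.05 in 13% (2-fold), 82% (4-fold) and over 99% (8-fold) of trials. Within the IVX-A12a group alone it was 4% to 5%. With no shift, the pooled rate was also about 5%.

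**The case against.** - **Standing of the analysis.** The coefficients appear in no visible primary or secondary objective or endpoint. The SAP tests no formal hypotheses. The choice of formulation is addressed by adjusted GMT and GMFR contrasts and seroresponse differences, which do not use them. This stands and limits the weight of the point.
- **Size.** At the only fold difference in the sample size section, 2-fold, the change is 0.01 to 0.05 for within-group coefficients of 0 or more. For strongly correlated pairs it stays small even at 8-fold. The protocol introduction describes the A and B subgroups of each virus as antigenically related, so a within-group value of 0 is a poor guess for those pairs. This stands. The 4- and 8-fold values in the SAP are thresholds for individual responders, not expected mean shifts.
- **Direction.** A reader might infer that pooling always inflates. It does not, as the unequal-shift cases show. The documents give no fold values, and the interim statement does not cover VLP core IgG. If that assay barely moves, a positive correlation involving it would be attenuated.
- **Other by-group analyses.** SAP 7.1.3 and 9.1.2 plan geometric mean ratios of A to B strain and of IgG to neutralizing fold-rise, by vaccine group. These help, but a mean ratio says nothing about how closely two responses vary together.
- **Reading of the text.** The 7.1 default gives some support to a by-group intention, the table shells are a separate document, and exploratory text is redacted. Pooling is still the natural reading of 9.1.1.3. If separate coefficients were meant, the sentence needs the same edit.

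**Conclusion.** The point holds in a limited form. As written, the Day 28, 180 and 365 coefficients include placebo and partly reflect vaccination status. The distortion is usually upward: 0.01 to 0.05 at an equal 2-fold shift, about 0.04 to 0.18 at 4-fold and 0.07 to 0.31 at 8-fold, largest for weakly related pairs. It can go downward when the two assays shift by very different amounts. The reader of a pooled figure cannot tell which applies. These sizes rest on an SD of 0.5 log10 in both assays, normal log titers, 80% vaccinated and one common shift in both IVX-A12 groups. Per-protocol exclusions would change the group sizes.

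Two stronger readings are tempting and not supported. One is that the trial's immunogenicity conclusions or the choice of IVX-A12a are undermined: nothing in the documents bases them on these coefficients. The other is that pooling would conceal interference between the RSV and hMPV antigens. The protocol does raise interference as a possibility, but neither document assigns the correlations to that question. Day 0 is unaffected.

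**What to change.** Replace the pooling instruction in SAP 9.1.1.3 with wording such as:

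*At Days 28, 180 and 365, Spearman coefficients will be calculated within each vaccine group. If a single figure is wanted, a partial Spearman correlation adjusted for vaccine group will be given, and any pooled coefficient will be labelled as including placebo. Day 0 may be pooled.*

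Section 9.1.2 refers back to 9.1.1.3, so it needs no separate change.

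No new data are needed; the program runs by group and the table gains rows. The price is precision. On the Fisher scale the 95% half-width near zero is about 1.96/√(n − 3): 0.12 for 250 pooled subjects, 0.20 for a group of 100 and 0.29 for the placebo group of 50. The group-adjusted partial coefficient recovers most of that precision where one summary per assay pair is enough.

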9.1.1.4. Outlier Detection

All titer outliers, for the PPS, will be listed using Tukey's method as described in [section 7.1.6](#) for Day 0 and Day 28 for serum anti-RSV/A-, RSV/B-, hMPV/A-, hMPV/B-specific NAb, and RSV and hMPV IgG prefusion F protein-specific antibody titers.

9.1.2. Secondary Immunogenicity Endpoint(s) and Analyses

The secondary immunogenicity endpoints are defined in [section 5.1.2.2](#). The definition of geometric mean fold rise (GMFR) is provided in [section 7.1](#).

This document is confidential.

The GMTs and adjusted GMTs for serum anti-RSV/A-, RSV/B-, hMPV/A- and hMPV/B-specific NAbs by live-virus assays at Days 180, and 365 will be calculated as described in [section 9.1.1.1](#). The RSV and hMPV prefusion F protein-specific IgG antibody titers by ELISA will also be calculated at Days 180 and 365 as described in [section 9.1.1.1](#). The analyses will be performed for the following:

- By vaccine group;
- By vaccine group and age subgroup analyses category;
- By vaccine group and baseline tertile;
- By vaccine group, baseline tertile and age subgroup analyses category.

GMTs, descriptive statistics, and 95% CIs will be produced for Day 0 for RSV/A-, RSV/B-, hMPV/A-, and hMPV/B- specific NAbs, and RSV and hMPV prefusion F protein-specific IgG antibody titers.

The GMFRs and adjusted GMFRs using ANCOVA (or ANOVA) for serum anti-RSV/A-, RSV/B-, hMPV/A-, and hMPV/B specific NAb ([live-virus assays]) and RSV and hMPV IgG prefusion F protein-specific antibody titers ([ELISAs]) and the ratios at Days 180, and 365 will be analyzed similarly as described in [section 9.1.1.1](#). The analyses will be performed for the following:

- By vaccine group;
- By vaccine group and age subgroup analyses category;
- By vaccine group and baseline tertile;
- By vaccine group, baseline tertile and age subgroup analyses category.

Data displays will also be produced for repeat titer and fold-rise box plots for Days 0, 180, and 365 as described in [section 9.1.1.1](#).

To assess the durability of RSV/A-, RSV/B-, hMPV/A-, and hMPV/B NAbs, and RSV and hMPV IgG prefusion F protein-specific antibody titers, the geometric fold-rise (decay) from Day 28 to Day 180 and Day 28 to Day 365 will be calculated. 95% CIs will be calculated by back transformation of the 95% CI for the mean of the log2 transformed individual fold rise computed using Student's t distribution. Median and quartiles of the fold-rise in antibody titer from Day 28 to Day 180 and Day 28 to Day 365 will also be displayed. The analyses will be performed for the following:

- By vaccine group;
- By vaccine group and age subgroup analyses category;
- By vaccine group and baseline tertile;
- By vaccine group, baseline tertile and age subgroup analyses category.

The geometric mean ratio (GMR) of the titers and fold-rise for serum anti-RSV/A- versus RSV-B will be calculated as described in [section 9.1.1.1](#) for all scheduled visits. Similarly, GMR will be produced for the ratio of serum anti-hMPV/A versus hMPV/B. This analysis will be performed for the following:

- By vaccine group;
- By vaccine group and age subgroup analyses category.

The GMR of the fold-rise in IgG prefusion F protein-specific antibody titer (ELISA) versus the fold rise in NAbs at all post-baseline visits for RSV and hMPV. This analysis will be performed for the following:

- By vaccine group;
- By vaccine group and age subgroup analyses category.

This document is confidential.

The proportion of subjects with ≥ 4 -fold increase in serum anti-RSV/A-, RSV/B-, hMPV/A- and hMPV/B-specific NAb versus baseline for Days 180 and 365 will be analyzed similarly as described in [section 9.1.2](#) by vaccine group, by vaccine group and age subgroup analyses category, by vaccine group and baseline tertile, and by vaccine group, baseline tertile, and age subgroup analyses category.

A similar analysis will be repeated for the proportion of subjects with ≥ 8 -fold increase for all post-baseline visits in serum anti-RSV/A-, RSV/B-, hMPV/A- and hMPV/B-specific NAb, as described in [section 9.1.1.2](#), for the following:

- By vaccine group;
- By vaccine group and age subgroup analyses category.

Tertile analyses will not be completed for ≥ 8 -fold increase.

Reverse cumulative distribution (RCD) curves will be provided for baseline (Day 0) to Days 28, 180, and 365 for the following assays: RSV/A-, RSV/B-, hMPV/A-, hMPV/B-specific NAb and RSV and hMPV prefusion F protein-specific IgG antibody titers. RCD curves will be produced for the following:

[figure not shown]
- By vaccine group;
- By vaccine group and age subgroup analyses category.

Analysis of correlation will be repeated, as described in [section 9.1.1.3](#), for Days 180 and 365.

Outliers will be listed, as described in [section 9.1.1.4](#), for Days 180 and 365.

To identify unknown RSV or hMPV infections, boxplots will be produced for serum anti-RSV/A-, RSV/B-, hMPV/A- and hMPV/B-specific NAb to display the fold-rise from Day 28 to Day 180, Day 28 to Day 365, and Day 180 to Day 365. The box plots will be produced for the PPS and will utilize log2 transformed fold-rise and back-transformed. Listings will also be generated for serum anti-RSV/A-, RSV/B-, hMPV/A- and hMPV/B-specific NAb, where fold increase ≥ 8 , from Day 28 to Day 180, Day 28 to Day 365, and Day 180 to Day 365. The listings will be produced for the FAS.

CCI

This document is confidential.

9.2. Observational Extension Trial Immunogenicity

No immunogenicity analysis will be performed for the observational extension trial due to early termination of the extension.

This document is confidential.

10. Safety

Safety will be presented separately for the main trial and observational extension trial.

10.1. Main Trial Safety

The safety analyses will be performed on the Safety Set and will include all data up to the end of the main trial, unless noted otherwise.

10.1.1. Adverse Events

Adverse events are collected as solicited, unsolicited AEs, SAEs, CESIs, and MAAEs. Solicited ARs are recorded in the subject diary; unsolicited AEs are collected on AE page of case report forms (CRFs). Furthermore, a solicited ARs that is ongoing after the diary period, leads to trial discontinuation, or results in an MAAE or SAE, should be entered on the AE page of the CRF as an unsolicited AE. The following are primary endpoints: Solicited local reactions and systemic ARs from the day of dosing (Day 0) through Day 6 (Study Day 1 to Study Day 7); Unsolicited AEs from day of dosing (Day 0) through 28 days post-vaccination (Study Day 1 to Study Day 29). SAEs, MAAEs and AEs leading to trial withdrawal from day of dosing (Day 0; Study Day 1) up to the end of the main trial, CESIs (mild, moderate or severe lower respiratory tract infection (LRTI) caused by RSV and/or hMPV) from day of dosing (Day 0; Study Day 1) up to the end of the main trial, and AESIs (including anaphylaxis, thrombocytopenia, and pIMCs, including Guillain Barre's syndrome, as defined in [section 16](#)) are secondary safety endpoints. AE summaries will be performed on the Safety Set, unless otherwise stated.

An overall summary of the number and percentage of subjects reporting any solicited ARs, Grade 3 solicited ARs, Grade 4 solicited ARs, \geq Grade 3 solicited ARs any unsolicited AEs, trial vaccine-related unsolicited AEs, Grade 3 unsolicited AEs, Grade 3 trial vaccine-related AEs, Grade 4 unsolicited AEs, Grade 4 trial vaccine-related AEs, \geq Grade 3 unsolicited AEs, \geq Grade 3 unsolicited AEs, SAEs, trial vaccine-related SAEs, CESIs, trial vaccine-related CESIs, AESIs (including pIMCs), trial vaccine-related AESIs (including pIMCs), MAAEs, trial-vaccine related MAAEs, AEs leading to trial discontinuation and AEs leading to death will be provided. The summary will be repeated by vaccine group and age subgroup analyses category.

A separate summary of the number and percentage of subjects reporting any AEs leading to main trial discontinuation, trial vaccine-related AEs leading to main trial discontinuation, SAEs leading to main trial discontinuation, trial vaccine-related SAEs leading to main trial discontinuation, CESIs leading to main trial discontinuation, trial vaccine-related CESIs related to main trial discontinuation, AESIs leading to main trial discontinuation, trial vaccine-related AESIs leading to main trial discontinuation, and MAAEs leading to main trial discontinuation, trial vaccine-related MAAEs leading to main trial discontinuation will also be provided. The summary will be repeated by vaccine group and age subgroup analyses category.

Listings will be provided for solicited ARs, unsolicited AEs, SAEs, CESIs, AESIs, MAAEs, non-RSV/hMPV LRTIs and AEs leading to main trial discontinuation for all data up to the end of the main trial. The listings will display study day, which is calculated as (event date – vaccination date + 1) if event date \geq vaccination date; and (event date – vaccination date) if event date $<$ vaccination date. AEs starting prior to the vaccination will be listed only and not included in summaries. A listing of solicited ARs, possibly reported incorrectly as unsolicited ARs, will also be included. If the solicited AR, possibly reported as an unsolicited AR, has a severity that is discrepant from the pre-defined diary, the discrepancy will also be reported.

This document is confidential.

